9.4 Data sources

This study will be conducted based on the InGef (former HRI) database which is an anonymized healthcare claims database covering all geographic regions of Germany. It includes longitudinal data from approx. 6.7 million Germans insured in one of approx. 64 German SHIs currently contributing data to the database (mainly company or guild health insurances).

Claims data are transferred directly from health care providers to a specialized data center owned by SHIs, which provides data warehouse and IT services. In the data center (acting as a trust center), data is anonymized before entering the InGef database. Data are anonymized with respect to individual insured members, health care providers (e.g. physicians, practices, hospitals, pharmacies), and the respective SHI. The most important data elements included in the database are displayed in Table 2. The time period covered by the database is limited to a look-back period of 6 years starting with the most current complete year of data (11).

Table 2 Information included	in the InGef Database
-------------------------------------	-----------------------

Demographics

Gender

Age

Date of death

	Region for place of living				
	Insurance status (e.g. retired, family insurance)				
	Date of insurance start and end (observation period)				
Outpatient Care	Diagnosis (ICD 10-GM Codes) and quarter in which the diagnosis was documented				
	Procedures performed (e.g. laboratory, radiology, echocardiography) (EBM-Codes) and day of performance				
	Type of specialist that documented the diagnosis and performed the procedure (e.g. cardiologist, general practitioner)				
	Costs of outpatient care				
Pharmacy	Drug dispensed by central pharmaceutical number (package level) – this is mapped to ATC codes and DDD's by InGef				
	Quantity dispensed				
	Day of prescription				
	Day of dispensing				
	Type of doctor prescribing (e.g. cardiologist, general practitioner)				
	Costs of drugs dispensed from SHI perspective (without individual rebates between single sickness funds and pharmaceutical companies)				
Hospital care	Main diagnosis (ICD 10-GM Codes) and additional diagnoses				
	Performed procedures and surgeries (e.g. pacemaker implant, implantable cardioverter defibrillator				
	Date of hospital admission				
	Reason for admission (e.g. accident, emergency, normal)				
	Date of end of hospital stay				
	Reason of end of hospital stay (e.g. death in hospital, normal end)				

	DRG-Code			
	Type of hospital: psychiatric vs. somatic			
Remedies and aids	Type of therapy (e.g. massage, occupational therapy, walker, wheel chair)			
	Quantity prescribed			
	Type of care provider			
	Start date			
	End date			
	Costs of therapy/aids			

9.5 Study size

Based on previous studies, we estimate a sample size of approximately 90,000 new users of oral anticoagulants (16,800 apixaban, 6,800 dabigatran, 1,600 edoxaban, 30,200 rivaroxaban and 35,400 phenprocoumon) with NVAF between 1st January 2013 to 30th June 2017. We used the event rates from a previous study based on the InGef research database (6) to estimate the expected number of ICH and IS/SE as primary study outcomes and the precision of the estimated expected events in users of all study drugs assuming an average follow-up time of 1 year per person. As edoxaban was not included in this study, we assumed the lowest event rate obtained for all NOACs to obtain conservative estimates

Table 3 Expected number of primary outcome events and corresponding precision assuming an						
average follow-up of one year per patient						

Overall		Intracranial hemorrhage			Ischemic stroke/systemic embolism			sm	
Oral anticoagulant	Estimated number of drug users	Estimated incidence rate	Expected events	Lower 95%- CI	Upper 95%- CI	Estimated incidence rate	Expected number of events	Lower 95%- CI	Upper 95%- CI
Phenprocoumon	35,400	0.007	248	218	279	0.025	885	828	944
Apixaban	16,800	0.004	67	52	84	0.027	454	413	496
Rivaroxaban	30,200	0.005	151	128	176	0.022	664	614	715
Edoxaban	1,600	0.004	6	2	12	0.022	35	24	48

9.6 Data management

Completely anonymized analysis datasets comprising all observations and variables required for the planned analyses will be created from the information contained exclusively within the InGef database. The analytic datasets will be person-level, and will contain variables as specified in 9.3.

It is required that all analyses are conducted on the site of the data provider due to data protection requirements. The central statistical software programs used by InGef to evaluate data are R and SAS Enterprise Guide.

9.7 Data analysis

9.7.1 Descriptive analysis

Descriptive statistics will be generated to summarize the baseline characteristics of the study population. For continuous variables, the mean, median as well as the corresponding standard deviation, upper and lower quartiles and the minimum and maximum will be reported. For categorical variables, absolute counts and proportions of patients with given characteristics will be calculated relative to the total sample size of each treatment group.

The incidence rates of IS/ SE (as combined endpoint), ICH, IS, SE, kidney failure, AKI, fatal bleeding, and severe IS will be reported overall as well as in all subgroups as the number of events per 100 person-years. Corresponding 95%-confidence intervals will be calculated assuming a Poisson distribution.

9.7.2 Main analysis

Analyses will be conducted in line with good statistical practices. Models will use confounding factors to adjust for group differences. However, unmeasured confounding and resulting confounding bias affecting point estimates, confidence intervals and any p-values in the treatment group comparisons may remain.

In a first step, Cox proportional hazards regression models will be applied in in each treatment group compared to phenprocoumon (reference) to estimate crude and confounder adjusted hazard ratios (HRs) of the above mentioned outcomes as well as treatment discontinuation (persistence) with accompanying 95% confidence intervals and *p*-values. Persistence (risk of non-persistence) will also be calculated separately for specific time points of interest (months 3, 6, 9, 12, 18 and 24). In the analysis of reduced vs. standard dose of NOACs, the standard dose will be used as reference. Kaplan-Meier cumulative incidence plots will be generated to characterize risk of outcome events of interest over time.

Information on confounding factors which are planned to be included in the models as well as in the estimation of the propensity score can be found in section 9.3.3.

In a second step, we will use the stabilized inverse probability of treatment weighting (IPTW) approach based on the propensity score to adjust for potential confounding resulting from imbalances in the baseline characteristics of different treatment groups. The objective of IPTW

based analysis is to create a weighted sample, for which the distribution of possible confounding variables is approximately the same between comparison groups (12,13). The propensity score is defined as the patient's probability to receive a treatment under investigation (i.e. phenprocoumon for main analyses and standard dose for the analyses of reduced vs. standard dose of NOACs) given a set of known patient's baseline characteristics. Propensity scores will be calculated using multiple logistic regression on a relevant set of patient characteristics listed in section 9.3.1 for each 1:1 comparison separately, e.g. rivaroxaban vs. phenprocoumon, rivaroxaban 15 mg vs. rivaroxaban 20 mg etc.

Let Z be an indicator variable relating to the treatment received by a patient, Z = 1 for an active treatment (e.g. rivaroxaban), Z = 0 for a control treatment (warfarin), and let X denote a vector of observed patient baseline characteristics. Then the propensity score is e = P(Z = 1|X). The inverse

probability of treatment weight is defined as $w = \frac{Z}{e} + \frac{1-Z}{1-e}$, i.e.

$$w = \frac{1}{e}$$
 for patients receiving the active treatment, and $w = \frac{1}{1-e}$ for patients receiving the control treatment.

Weighting by the inverse probability of treatment results in an artificial population or synthetic sample, in which treatment assignment is independent of measured baseline characteristics. Of note, a very low propensity score of subjects receiving an active treatment, or a propensity score close to 1 of subjects receiving a control treatment result in large weights. Such weights increase the variability of the estimated treatment effect (12). Moreover, it is known that the sample size of the synthetic sample is always greater that the sample size of the original data. Consequently, regression estimates with IPTW tend to have smaller confidence intervals because of the inflated sample sizes. In our analysis we will use IPTW with stabilized weights (12,13) which ensure more robust effect estimates. The stabilized weight is defined as $sw = \frac{P(Z=1)*Z}{e} + \frac{(1-P(Z=1))*(1-Z)}{1-e}$. The use of stabilized weights in the synthetic data preserves the sample size of the original data set (12). The application of propensity score methods via stabilized weights requires overlap of the propensity score distribution in the active and control treatment group. Therefore distributions of propensity scores will be inspected for original data and the synthetic sample. Furthermore, the distribution of stabilized weights in the original data will be examined to determine, if large weights remain after stabilization of weights. By applying IPTW method using the propensity score assessment needs to be done, whether weighting procedure succeeded to balance patient characteristics between treatment groups. The distributions of propensity scores and stabilized weights will be inspected for original data and the synthetic sample. The balance of patient characteristics between treatment groups will be checked by using standardized mean differences (SMD). An absolute SMD of 0.1 or less will be considered as a negligible difference between groups. For continuous variables, the SMD is calculated via

$$SMD_{cont} = \frac{\overline{X_T} - \overline{X_C}}{\sqrt{\frac{S_T^2 + S_C^2}{2}}},$$

Where $\overline{X_T}$, S_T^2 and $\overline{X_C}$, S_C^2 denote the weighted sample mean and weighted sample variance of the variable in the treated and control patients, respectively. For binary variables, the SMD is calculated by

$$SMD_{cat} = \frac{100(P_T - P_C)}{\sqrt{(P_T(1 - P_T) + P_C(1 - P_C))/2}},$$

Where P_T and P_C denote the weighted sample prevalence of the variable in the treated and control patients, respectively.

In a third step, we will additionally conduct a propensity score matched analyses for each comparison. A 1:1 matching will be performed using the nearest-neighbor approach with a caliper of 0.2 without replacement. Again, the balance of patient characteristics between treatment groups will be checked in analogy to the description above.

For the analysis of IS /SE as combined endpoint and ICH (primary objectives) as well as for the comparison of reduced vs. standard dose of NOACs (other objectives) all three approaches will be used, i.e. Cox proportional hazards regression models, IPTW and propensity-score matching. For all other analyses (secondary objectives) only Cox proportional hazards regression models and IPTW will be applied.

To describe the risk of recurrent hospitalizations and IS/ SE, the following analyses will be conducted. Analyses of recurrent events will be conducted for the unadjusted, matched as well as IPTW populations:

1) Mean cumulative function (MCF)

An important quantity is the mean number of recurrent events per subject by a certain time, i.e. the mean cumulative function (MCF) which is defined as

$$\mu(t) = E(N(t)).$$

The MCF is a marginal quantity, i.e. independent of the history of the event process. The common Nelson-Aalen estimator for survival analysis can be used as a non-parametric estimator for the MCF under the assumption of independent censoring, i.e. patients remaining are representative of the population.

Let $Y_i(t)$ indicate whether patient i = 1, ..., m is "at risk" for an event at time t and $Y_{\Sigma}(t) = \sum_{i=1}^{m} Y_i(t)$ the total number of patients at risk at time t. With $dN_{\Sigma}(t) = \sum_{i=1}^{m} Y_i(t)dN_i(t)$ being the total number of events at time t and H distinct event times across all m patients denoted as $t_1 \leq \cdots \leq t_H$ the Nelson-Aalen estimator is given as

 $\hat{\mu}(t) = \sum_{h:t_h \le t} \frac{dN_{\Sigma}(t_h)}{Y_{\Sigma}(t_h)}.$

In SAS the Nelson-Aalen estimator for the MCF can be calculated by means of the PHREG procedure. The following code plots the estimated MCFs of several treatment groups in one graph:

```
PROC PHREG DATA=dataset PLOTS(OVERLAY=ROW)=MCF;
MODEL (TStart,TStop) * Status(0)= ;
* start/stop time of inter-event times and censoring
identifier;
STRATA trt; * treatment group identifier;
RUN;
```

2) Andersen-Gill Model (AG) with robust standard errors (Wei Lin Weissfeld Model)

The Wei Lin Weissfeld (WLW) model models the total time from randomization to 1^{st} , 2^{nd} , 3^{rd} , ..., k-th event. Before applying the WLW model one has to pre-specify the maximum number of events k one wants to analyze. Therefore, one has to arrange the data in the right structure (a semi-restricted risk set) and also make sure to create 'dummy' events for patients with fewer than the maximal number of events k.

Semi-restricted risk sets

Semi-restricted risk sets have event-specific baseline hazards but allow subjects who have less than (k-1) events to be at risk for the *k*-th event through the creation of 'dummy' risk intervals. Thus a subject who has had none or one event can be considered at risk of a fourth event. However, a semi-restricted risk set does not allow information from the *k*-th event risk interval to contribute to the risk set for an earlier event. This risk set only applies to the total time and counting process formulation with event-specific baseline hazards.

[figure not shown]

Figure 2 Hypothetical example with total time risk intervals

ID	time	num	event	total		total cp	
				start	stop	start	stop
Α	2	1	1	0	2	0	2
Α	5	2	1	0	5	2	5
A	13	3	0	0	13	5	13
в	7	1	1	0	7	0	7
в	11	2	1	0	11	7	11
в	17	3	1	0	17	11	17
С	14	1	0	0	14	0	14
С	14	2	0	0	14	0	14
С	14	3	0	0	14	0	14

Figure 3 Semi-restricted risk sets in dataset representation

For example, in total time subject B is included with the second event time and subject C is included with a 'dummy' risk interval in the risk set for the second event of subject A (Figure 1). In the example above the maximum number of events per patient is three (for subject B). Accordingly, two dummy risk intervals need to be included for subject C for 'dummy' event number two and three. This results in a dataset as displayed in Figure 2.

One treatment effect estimate, which can be seen as an 'average effect' will be obtained. This average effect, however, is difficult to interpret, as for example the effect on the second event already includes the effect on the first event. Averaging the WLW treatment effects for first and second event would thus seem to double-count the effect on the first event.

Therefore, it is generally more advisable to obtain event-specific estimates by means of specifying interactions in the PROC PHREG call routine, i.e. treatment by event number. The following code gives an example of this for k = 3.

```
PROC PHREG DATA=<dataset> COVSANDWICH(AGGREGATE);
MODEL totstop*event(0) = treat1 treat2 treat3;
treat1 = treat*(num=1);
treat2 = treat*(num=2);
treat3 = treat*(num=3);
STRATA num;
ID pid;
RUN;
```

The event-specific estimate for the first event then coincides with the estimate of the Cox proportional hazards model for time-to-first event.

The distinctive feature of the WLW model is that each individual's time at risk for each event is considered to study entry, so that study entry is 'preserved' for all event-specific analyses.

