9.3.3 Covariate definition

All demographic and clinical characteristics will be assessed based on primary and secondary hospital diagnoses and verified ambulatory diagnoses (ICD-10 GM codes), OPS codes, EBM codes and ATC codes as defined in Annex 3: Additional information. Unless otherwise mentioned, all information on covariates will be collected in the baseline period., i.e. in the 365 days prior to the index date). The assessment date for hospital diagnoses will be the admission date of the respective hospitalization and for ambulatory diagnoses the date of the first encounter with the diagnosing physician in the respective quarter (as ambulatory diagnoses are available on a quarterly basis only). Data derived from OPS codes and EBM codes will be assessed on the exact date.

Demographic characteristics

- Gender at index date
- Age at index date
- Age at index date categorized: 18–39, 40–44, 45–49, ..., 85-89, 90+ years

Clinical characteristics

- CHADS₂ score
- CHA₂DS₂-VASc score
- modified HAS-BLED score (the INR will not be included in the calculation of the score because this information is not available in the InGef database, end-stage renal disease will not be considered as these patients will be excluded from the analysis)
- Comorbidities
 - o Alcohol abuse
 - o Anemia
 - Aortic plaque
 - o Anemia
 - Coronary heart disease
 - Angina pectoris
 - Myocardial infarction
 - Acute ischemic heart diseases
 - Chronic ischemic heart disease
 - Coronary artery bypass graft(s)
 - Percutaneous coronary intervention
 - o Dementia
 - o Depression
 - o Diabetes mellitus
 - o Drug abuse
 - o Gastric or peptic ulcer disease/diseases of gastrointestinal tract
 - o Heart failure
 - History of major bleeding (hospitalization only)
 - o Hypertension
 - Hypothyroidism

- o Inflammatory bowel disease
- IS or transient ischemic attack
- Other cerebrovascular disease
- o Liver disease
- o Hyperlipidemia
- o Volume depletion
- Other metabolic disorders
- o Obesity
- Peripheral arterial disease
- o Psychosis
- o Pulmonary disease
- o Rheumatoid arthritis/collagen vascular disease
- Tobacco abuse
- o Other vascular disease
- Malignant cancer (except non-melanoma skin cancer)
- Comedications
 - o Angiotensin-converting enzyme inhibitors or angiotensin-receptor blockers
 - o Antiarrhythmics
 - o Antidepressants
 - o Antiplatelets
 - Antiulcer drugs (except proton-pump inhibitors)
 - o Calcium channel blockers
 - o Diabetes drugs
 - o Diuretics

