 - o Erythropoietin-simulating agents
 - o Estrogens
 - o Lipid modifying agents
 - Non-steroidal anti-inflammatory drugs
 - o Proton-pump inhibitors
- Other indicators of overall health status

- Number of hospitalizations
- Number of different medications used (based on 7 digit ATC codes)
- o Number of ambulatory physician visits

Others

- Year of cohort entry
- Duration of follow-up in days
- Type of cohort exit (end of study period, switch, discontinuation, death, etc.)

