9.3.4 Subpopulations and Subgroups

Subgroups and subpopulation are only build on the basis of conditions already present at index date.

The following subpopulations of special interest will be defined:

• Patients with renal impairment initiating either phenprocoumon or reduced doses of NOACs

Patients with renal impairment will be identified based on primary and secondary hospital diagnoses or verified ambulatory diagnoses in the baseline period according to Fleet et al. (9) and Nielsen et al. (4) (see definition of renal impairment as covariate in Annex 3: Additional information).

• Patients with chronic renal disease initiating either phenprocoumon or reduced dose of NOACs

Patients with chronic renal disease will be identified based on primary and secondary hospital diagnoses or verified ambulatory diagnoses (ICD 10 GM code N18.3 and N18.4) in the baseline period.

The following subgroups of special interest will be defined. Analyses will be conducted also including a test for effect modification (interaction):

• Frail patients

Frailty can be operationalized in several ways, but is commonly characterized by a set of signs and symptoms in geriatrics and gerontology research. While difficult to assess in administrative claims data, the recently validated claims based Frailty Indicator (10) will be used in this study. This algorithm is

validated using against the frailty phenotype, which is the most widely used instrument for assessing frailty. The frailty cut-off for this study will be 0.25 as the desire is to specifically identify frail individuals.

• Age group (<=79 vs. 80+ years)

Age will be assessed at the index date.

• Renal impairment

Patients with renal impairment will be identified based on primary and secondary hospital diagnoses or verified ambulatory diagnoses in the baseline period according to Fleet et al. (9) and Nielsen et al. (4) (see definition of renal impairment as covariate in Annex 3: Additional information).

• Prior IS or SE

Patients with IS, TIA or SE will be identified based on primary and secondary hospital diagnoses or verified ambulatory diagnoses in the baseline period according the definition for IS/TIA and SE as covariate (see Annex 3: Additional information).

• Reduced vs. standard dose of NOACs

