K27.4, K27.6, K28.0, K28.2, K28.4, K28.6, K29.0, K62.5, K66.1 K92.0, K92.1. K92.2, M25.0, N02, N42.1, N83.6, N85.7, N89.7, N93.0, N93.8, N93.9, N95.0, R04.0, R04.1, R04.2, R04.8, R04.9, R23.3, R31, R58, S06.4, S06.5, S06.6, S06.8

Section 9.3.3. Covariate definition

Operational definition of CHA2DS2-VASc Score:

Conditions	ICD-10 GM code	Assigned weights
Hypertension	I10 – I15, I67.4	1
Diabetes mellitus	E10 – E14	1
Heart failure	I11.0, I13.0, I13.2, I25.5, I42, I43, I50, I09.9	1
Age between 65 and 74 years		1
Vascular disease (previous MI, peripheral arterial disease or aortic plaque)	I21 – I23, I25.2, I70.0, I70.2 – I70.9, I71, I73.9	1
Stroke or TIA	G45.0 – G45.2, G45.4 – G45.9, I63, I69.3, I69.4, I64	2
Age \geq 75 years		2
Female sex		1

Operational definition of CHADS₂ Score:

Conditions	ICD-10 GM code	Assigned weights
Hypertension	I10 – I15, I67.4	1
Diabetes mellitus	E10 – E14	1
Heart failure	I11.0, I13.0, I13.2, I25.5, I42, I43, I50, I09.9	1
Stroke or TIA	G45.0 – G45.2, G45.4 – G45.9, I63, I69.3, I69.4, I64	2

Age ≥ 75	years
---------------	-------

1

Operational definition of modified HAS-BLED Score:

Criteria	ICD-10 GM / ATC /OPS code	Assigned weights
Hypertension	I10 – I15, I67.4	1
Liver or renal disease	B18.0, B18.1, B18.2, I85, K70.0, K70.2, K70.3, K70.4, K70.9, K72.1, K73, K74, K75.4, K75.8, K76.0, K76.6, K76.9, Z94.4, D63.1, E10.2, E11.2, E13.2, I12, I13, N02, N03, N04, N05, N07, N08, N14, N18.1-N18.4, N18.9, N19, Q61	1
Stroke history	I63, I69.3, I69.4, I64	1
Major bleeding event	OPS: 8800 ICD-GM: D62, H21.0, H31.3, H35.6, H43.1, H45.0, I32.1, I60 - I62, J94.2, M25.0, S06.4, S06.5, S06.6, S06.8	1
Alcohol abuse	F10	1
Non-steroidal anti-inflammatory drugs or antiplatelet	B01AC, M01A*	1
Age >65		1

Operational definition of claims based frailty indicator (10):

Criteria	ICD-10 GM / ATC /OPS code	Assigned weights
Impaired mobility	U50, Z99.3	1
Depression	F31, F32 – F34, F39, F43.1, F43.2,	1
Congestive heart failure	I11.0, I13.0, I13.2, I25.5, I42, I43, I50	
Parkinson's disease	G20-G22	

White race (yes vs. no)	N/A	
Arthritis (any type)	M05, M06, M08, L90.0, L94.0, L94.1, L94.3, M32 – M35, M45, M46, M48, M49	
Cognitive impairment	F01 – F05, F06.0, F06.7, F06.8, F07.0, F07.8, F09, G30, G31.0, G31.1, G31.8, R41	
Charlson comorbidity index (>0, 0)	As defined above	
Stroke	I60-I64, I69.0-4	1
Paranoia	F06.0, F06.2, F20, F22-F29, F32.3, F33.3, F44.8	
Chronic skin ulcer	170.24, 170.25, 183.0, 183.2, 187.21, L89, L97	
Male (yes vs. no)		

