ICD-GM: D63.1, E10.2, E11.2, E13.2, I12, I13, N02, N03, N04, N05, N07, N08, N14, N18.1-N18.4, N18.9, N19, Q61

- Acute kidney injury: ICD-GM: N17
- Tobacco abuse: ICD-GM: F17.2
- Other vascular disease: ICD-GM: I70.1, I72, I73.1, I73.8, I74, I79, K55.1, K55.8, K55.9, Z95
- Malignant cancer (excl. non-melanoma skin cancer) : ICD-GM: C00-C97 (excl. C44)
- Angiotensin-converting enzyme inhibitors or angiotensin-receptor blockers: ATC: C09
- Antiarrhythmics:

ATC: C01B

• Antidepressants:

ATC: N06A

- Antiplatelets: ATC: B01AC
- Antiulcer drugs (except proton-pump inhibitors): ATC: A02BA, A02BB, A02BX
- Beta blockers:

ATC: C07

- Calcium channel blockers: ATC: C08
- Diabetes drugs (incl. insulin): ATC: A10A, A10B
- Diuretics:

ATC: C03

- Erythropoietin-simulating agents: ATC: B03XA
- Estrogens: ATC: G03C, L02AA
- Lipid modifying agents: ATC: C10

- Non-steroidal anti-inflammatory drugs: ATC: M01A
- Proton-pump inhibitors:

ATC: A02BC

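### The adjustment set is stated inconsistently on kidney variables, and coded CKD stage is a covariate nowhere, so the primary renal comparison may stay confounded by measured severity

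*Protocol*

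**What the plan says.** Protocol Section 9.7.2 names Section 9.3.3 as where the "confounding factors which are planned to be included in the models as well as in the estimation of the propensity score can be found". A few lines later it says that propensity scores are estimated on "a relevant set of patient characteristics listed in section 9.3.1". Section 9.3.1 is the exposure definition and lists no patient characteristics.

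The comorbidity list in 9.3.3 runs from "Rheumatoid arthritis/collagen vascular disease" straight to tobacco abuse. It has no item for renal impairment, CKD stage, AKI or systemic embolism, and the comedication list has no beta blockers. Kidney disease appears only inside the modified HAS-BLED score, for which 9.3.3 notes that "end-stage renal disease will not be considered as these patients will be excluded from the analysis".

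9.3.3 also says that its characteristics are assessed as defined in Annex 3. The part of Annex 3 headed for Section 9.3.3 gives codes for renal impairment, AKI (N17), systemic embolism (I74) and beta blockers (C07). Renal impairment is one pooled item whose code list ends with "N18.1-N18.4, N18.9, N19, Q61". Section 9.3.4 treats it as a covariate too: "see definition of renal impairment as covariate in Annex 3: Additional information".

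Under *Others*, the 9.3.3 list also carries duration of follow-up and "Type of cohort exit (end of study period, switch, discontinuation, death, etc".

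**The concern.** A programmer who follows 9.7.2 to 9.3.3 builds models without a stand-alone renal item. One who follows Annex 3 builds models with it. One who follows the propensity score pointer to 9.3.1 finds nothing. The protocol states the adjustment set, and states it in ways that do not agree.

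The protocol itself says why kidney function matters for treatment choice. Section 7 notes that clinicians hesitate to use NOACs even in moderate renal impairment, and Section 9.9 ties the reduced rivaroxaban dose to a range of filtration rate. Kidney failure and AKI are secondary outcomes, for which baseline renal disease and prior AKI are obvious confounders.

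For the primary comparison the question is narrower. Everyone has renal impairment, so what can still differ between arms is its severity. Section 9.3.4 sets starters of reduced-dose NOACs against all renally impaired starters of phenprocoumon, at any stage below end-stage. Cox adjustment, weighting and matching draw on the same covariates, so none of them makes up for a variable missing from all three. Balance checks limited to the listed variables would not show an imbalance in stage.

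**Working it through.** The plan states no figure on this point, so there is none to reproduce. The check is a comparison of lists, followed by an illustration on assumed inputs.

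**Step 1. The two lists side by side**

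| Item | 9.3.3 list | Annex 3, part for 9.3.3 |
|---|---|---|
| Renal impairment | absent | defined, one yes/no item |
| Prior AKI | absent | defined (N17) |
| Systemic embolism | absent as an item | defined (I74) |
| Beta blockers | absent | defined (C07) |
| CKD stage | absent | absent |

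I74 is also among the codes for other vascular disease, which is in both lists, so systemic embolism is partly captured.

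**Step 2. What HAS-BLED carries**

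Annex 3 gives one point for "Liver or renal disease". The renal codes in that row are the same as those of the renal impairment covariate, from D63.1 to Q61.
- Overall population: the point varies, but it is shared with liver disease and summed into a total score.
- Renal-impairment population: every patient has at least one of these codes, so the point is 1 for all. A yes/no renal flag is constant too. Neither can adjust for anything, so adding the Annex 3 flag to 9.3.3 does not help the primary analysis.

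**Step 3. Where stage is used**

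N18.3 and N18.4 appear in 9.3.4 to define a separate chronic renal disease subpopulation. Stage is therefore held in the data. It enters no model, and inside that subpopulation the split between N18.3 and N18.4 is also unadjusted.

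**Step 4. Possible size (assumptions)**

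For an omitted binary confounder, the ratio is multiplied by B = [1 + p1(RR − 1)] / [1 + p0(RR − 1)], where p1 is its prevalence on the NOAC, p0 its prevalence on phenprocoumon, and RR its effect on the outcome. The documents give none of these for this cohort. All values below are assumed, with p1 on both sides of p0.

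| Omitted variable | p1 | p0 | RR 1.25 | RR 1.5 | RR 2.0 |
|---|---|---|---|---|---|
| Renal impairment, overall | 0.15 | 0.28 | 0.970 | 0.943 | 0.898 |
| Renal impairment, overall | 0.35 | 0.28 | 1.016 | 1.031 | 1.055 |
| Advanced stage, primary | 0.05 | 0.15 | 0.976 | 0.953 | 0.913 |
| Advanced stage, primary | 0.20 | 0.15 | 1.012 | 1.023 | 1.043 |

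Examples at RR 2.0: 1.15/1.28 = 0.898 and 1.05/1.15 = 0.913. The formula assumes no adjustment through any other covariate, so these factors are outer values for the chosen inputs.

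**Step 5. Can the documents fix the RR?**

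The nearest figures are phenprocoumon rates per 100 person-years: the renal subgroup of the earlier study (Section 7, Figure 1) against the overall rates in Table 3 (2.5 for stroke/systemic embolism, 0.7 for ICH).
- One-tablet-per-day exposure: stroke 3.39/2.5 = 1.36; ICH 0.99/0.7 = 1.41.
- Empirical daily dose exposure: stroke 2.46/2.5 = 0.98; ICH 0.86/0.7 = 1.23.

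The answer depends on the exposure definition, and the stroke ratio compares stroke alone with stroke plus systemic embolism. These figures do not establish an RR.

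**The case against.** **Renal impairment and AKI are in the document.** 9.3.3 refers to Annex 3, Annex 3 defines both as covariates, and 9.3.4 calls renal impairment a covariate. The 9.3.3 list also prints anemia twice, which suggests careless transcription. This stands. A reader might infer that the sponsor plans to leave kidney function out of adjustment, but the text does not support that. For these items the defect is a contradiction between list and annex.

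**Severity is partly handled.** End-stage disease and dialysis are excluded in all arms, and the N18.3/N18.4 subpopulation restricts stage. This stands in part: restriction there does not adjust the primary comparison, which includes N18.1, N18.2 and unspecified disease.

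**Residual confounding is disclosed.** Sections 9.7.2 and 9.9 warn of it and note the missing laboratory values. That covers what cannot be measured. Coded stage can be, and 9.3.4 already uses it.

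**Other covariates act as proxies.** Anemia, diabetes, hypertension, heart failure, diuretics and erythropoietin agents are listed. They would shrink the factors in Step 4 but do not replace stage.

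**Post-index items.** A reader might infer that follow-up time and exit type will be adjusted for. 9.7.2 limits the propensity score to baseline characteristics, which excludes them there. The Cox models lack such an explicit limit, so a label is useful, but this is minor.

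**Conclusion.** The point holds as an inconsistency plus one real gap. The adjustment set is given in sources that disagree on four variables, with a wrong pointer for the propensity score. If 9.3.3 is applied as written, the overall-population analyses carry kidney function directly only through a shared HAS-BLED point, although AKI and kidney failure are outcomes. Coded CKD stage is a covariate nowhere, and in the primary population the remaining direct renal terms are constant. The primary comparison may therefore stay confounded by severity that the data record.

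Size and direction are unknown. On the assumed inputs the hazard ratio would be multiplied by about 0.90 to 1.06 overall and 0.91 to 1.04 in the primary population, less with partial adjustment. For scale only, the earlier study in the same database reported 0.86 (0.76 to 0.97) for rivaroxaban on stroke/systemic embolism.

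A reader might infer that the bias favours the NOACs. That needs renal impairment, or advanced stage, to be less common on the NOAC, which the documents do not show. Dividing the earlier study's 9,871 renally impaired phenprocoumon patients by this study's projected 35,400 users gives 28%, but it mixes two cohorts and is not a prevalence; 0.28 is used above only as an assumption.

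**What to change.** 1. Add renal impairment, prior AKI (N17), systemic embolism and beta blockers to the 9.3.3 list so that it matches Annex 3.
2. In 9.7.2, change the propensity score pointer from 9.3.1 to 9.3.3.
3. Require renal impairment and prior AKI in every Cox and propensity score model in which they vary.
4. Add coded CKD stage as a categorical covariate (N18.1, N18.2, N18.3, N18.4, unspecified/other) to 9.3.3 and Annex 3, above all for the renal populations, and report its standardized mean difference before and after weighting or matching.
5. Mark duration of follow-up and type of cohort exit as descriptive only.

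The cost is protocol and SAP wording; the codes are already named in the protocol and available in the database. The limit is that stage will be unspecified for some patients, so some residual confounding by severity will remain and should be stated in Section 9.9.
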